3.1 Characteristics

This is a single-center Phase 1b open-label, study of PSMA-targeted radionuclide therapy with ¹⁷⁷Lu-PSMA-617 in combination with pembrolizumab in patients with mCRPC who have previously progressed on at least one prior androgen pathway inhibitor (e.g. abiraterone, enzalutamide, apalutamide). Patients must have at least three metastatic lesions which are PSMA-avid on baseline ⁶⁸Ga-PSMA-11 PET imaging.

In **Part A** of the study, patients will be enrolled in sequential fashion to one of treatment schedules with respect to timing of ¹⁷⁷Lu-PSMA-617 in relation to first dose of pembrolizumab (N = 6 evaluable patients per schedule):

Schedule 1) Priming dose of ¹⁷⁷Lu-PSMA-617 administered on Cycle 1 Day 1 followed by pembrolizumab 200 mg IV q 21 days starting Cycle 2 Day 1.

Schedule 2) Priming dose of ¹⁷⁷Lu-PSMA-617 administered concurrently with initiation of pembrolizumab on Cycle 1 Day 1.

Schedule 3) Priming dose of ¹⁷⁷Lu-PSMA-617 administered on Cycle 1 Day 1 following initiation of pembrolizumab on Cycle 1 Day -21.

The priming dose of ¹⁷⁷Lu-PSMA-617 will be 7.4 +/- 15% GBq, which is the recommended phase 3 dose of the agent. If the DLT frequency exceeds 33% including patients across the three schedules, Dose Level -1 of ¹⁷⁷Lu-PSMA-617 will be investigated (4 Gbq +/- 15%).

6 evaluable patients will be enrolled in each of the three cohorts in sequential fashion in Part A of the study. The DLT window will be Cycle 1 + Cycle 2. If the DLT frequency is \geq 33% for a

particular cohort, that dosing schedule will be determined to be non-tolerable and the next schedule will be evaluated. In addition, if the DLT frequency attributable specifically to Lu-PSMA-617 is $\geq 33\%$ after 6 or more evaluable patients are enrolled in Part A of the study, the dose of Lu-PSMA-617 will be reduced to Dose Level -1 (4 GBq +/- 15%) for the remainder of patients enrolled on study. If the DLT frequency attributable to Lu-PSMA-617 at Dose Level -1 is $\geq 33\%$ after 6 or more patients are treated at Dose Level -1, study accrual will be halted.

Using the data obtained in Part A, the recommended phase 2 dose and schedule of ^{177}Lu -PSMA-617 will be determined by the DSMC and Principal Investigator using a combination of safety, efficacy, and immunologic effects of treatment from the first two cycles (and additional cycles of treatment when available).

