(9) No other systemic anti-cancer therapies administered other than LHRH analogue within 14 days, or 5 half-lives, whichever is shorter, prior to initiation of study treatment. Adverse events related to prior anti-cancer treatment other than LHRH analog treatment must have recovered to Grade ≤ 1 with the exception of any grade alopecia and grade ≤ 2 neuropathy.

(10) Patients must have an ECOG performance status of 0 or 1.

(11) Patients must use appropriate methods of contraception during study treatment and for at least 60 days after last study treatment.

- Patients who are sexually active should consider their female partner to be of childbearing potential if she has experienced menarche and is not postmenopausal (defined as amenorrhea > 24 consecutive months) or has not undergone successful surgical sterilization. Even women who

use contraceptive hormones (oral, implanted, or injected), an intrauterine device, or barrier methods (diaphragms, condoms, spermicide) should be considered to be of childbearing potential.

- Patients who have undergone vasectomy themselves should also be considered to be of childbearing potential.
- Acceptable methods of contraception include continuous total abstinence, or double-barrier method of birth control (e.g. condoms used with spermicide, or condoms used with oral contraceptives). Periodic abstinence and withdrawal are not acceptable methods of contraception.

(12) Patients must provide consent to comply to recommended radioprotection precautions during study

(13) Patients willing to undergo tumor biopsy and have at least one lesion safely accessible to tumor biopsy. Bone or soft tissue lesion is allowed.

(14) Measurable disease by RECIST 1.1 criteria

Exclusion Criteria

- (1)** Untreated brain metastases at study entry. Patients with previously treated brain metastases are eligible provided the following criteria are all met:
 - Last treatment was > 28 days prior to C1D1
 - No evidence of new/progressive brain metastases is observed on MRI obtained during Screening window
 - Patient is clinically stable without requirement of steroid treatment for at least 14 days prior to first dose of study treatment.
- (2)** Receipt of prior PSMA-directed treatment (e.g. radiotherapy, immunotherapy, or antibody-drug conjugate).
- (3)** Prior enrollment on clinical study investigating Lu-PSMA-based radioligand therapy
- (4)** Prior treatment with radium-223 or other radioisotope for the treatment of prostate cancer.

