- (5)** Has received prior radiotherapy within 2 weeks of start of study treatment. Participants must have recovered from all radiation-related toxicities, not require corticosteroids, and not have had radiation pneumonitis. A 1-week washout is permitted for palliative radiation (≤ 2 weeks of radiotherapy) to non-CNS disease.
- (6)** Receipt of prior pembrolizumab or another immune checkpoint inhibitor (e.g. nivolumab, ipilimumab).

(7) Is currently participating in or has participated in a study of an investigational agent or has used an investigational device within 4 weeks prior to the first dose of study treatment.

Note: Participants who have entered the follow-up phase of an investigational study may participate as long as it has been 4 weeks after the last dose of the previous investigational agent.

(8) Receipt of taxane chemotherapy applied in the castration-resistant setting. Prior receipt of taxane chemotherapy in the hormone-sensitive setting is allowed.

(9) Grade > 2 peripheral neuropathy at the time of study entry

(10) Has severe hypersensitivity (\geq Grade 3) to pembrolizumab and/or any of its excipients.

(11) Has an active autoimmune disease that has required systemic treatment in the past 2 years (i.e., with use of disease modifying agents, corticosteroids or immunosuppressive drugs). Replacement therapy (e.g., thyroxine, insulin, or physiologic corticosteroid replacement therapy for adrenal or pituitary insufficiency) or treatment with drugs (e.g. neomercazol, carbamazole, etc.) that function to decrease the generation of thyroid hormone by a hyperfunctioning thyroid gland (e.g. in Graves' disease) is not considered a form of systemic treatment of an autoimmune disease.

(12) Has a diagnosis of immunodeficiency or is receiving systemic steroid therapy at a prednisone equivalent dose of > 10 mg daily or other form of immunosuppressive therapy within 7 days prior to first dose of study drug.

(13) Has a history of (non-infectious) \geq grade 2 pneumonitis/interstitial lung disease that required steroids within past 2 years or has current \geq grade 1 pneumonitis/interstitial lung disease at the time of study enrollment.

(14) Has received a live vaccine or live-attenuated vaccine within 30 days prior to the first dose of study drug. Administration of killed is allowed.

(15) Patients who because of age, general medical or psychiatric condition, or physiologic status cannot give valid informed consent.

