Grades 3 or 4	Stop Infusion. Grade 3: Prolonged (i.e., not rapidly responsive to symptomatic medication and/or brief interruption of infusion); recurrence of symptoms following initial improvement; hospitalization indicated for other clinical sequelae (e.g., renal impairment, pulmonary infiltrates) Grade 4: Life-threatening; pressor or ventilatory support indicated	No subsequent dosing Additional appropriate medical therapy may include but is not limited to: IV fluids Antihistamines NSAIDS Acetaminophen Narcotics Oxygen Pressors Corticosteroids Epinephrine Increase monitoring of vital signs as medically indicated until the subject is deemed medically stable in the opinion of the investigator. Hospitalization may be indicated. Subject is permanently discontinued from further trial treatment administration.
Appropriate resuscitation equipment should be available in the room and a physician readily available during the period of drug administration.		

5 Study Procedures

A written, signed, informed consent form (ICF) and a Health Insurance Portability and Accountability Act (HIPAA) authorization must be obtained before any study-specific assessments are initiated. A copy of the signed ICF will be given to the subject and a copy will be filed in the medical record. The original will be kept on file with the study records.

The Study Calendar summarizes the trial procedures to be performed at each visit according to the assigned Treatment Schedule (Schedule 1, Schedule 2, or Schedule 3, respectively). Screening assessments must be performed within 28 days prior to the initiation of protocol therapy. Any results falling outside of the reference ranges may be repeated at the discretion of the investigator. All on-study procedures are allowed a window of \pm 3 days unless otherwise noted. Treatment or visit delays for public holidays or weather conditions do not constitute a protocol violation.

Individual trial procedures are described in the study schedule below. It may be necessary to perform these trial procedures at unscheduled time points if deemed clinically necessary by the investigator.

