5.2 Study Calendar: Schedule 1 (¹⁷⁷Lu-PSMA-617 prior to Pembrolizumab)

	Screening (Day -28 to -1 unless otherwise noted)	Treatment				End of Treatment	Safety Follow up			
		Cycle 1			Cycle 2+ (+/- 3 days unless otherwise noted)		D1 (+/- 3 days)	+ 21 days	30 Days (+/- 7 days) post-last dose	
		D1 (-3 days)	D2	D8 (+/- 1 day)						
Informed consent	x									
Medical history	x									
Baseline conditions	x									
Concurrent medications	x	x		x	x	x	x	x	x	
Height	x									
Weight	x	x		x	x	x	x	x	x	
ECOG Performance status	x	x		x	x	x	x	x	x	
Physical exam and vital signs	x	x		x	x	x	x	x	x	
CBC and Serum Chemistry Panel^{1,2}	x	x		x	x	x ³	x	x	x	
Thyroid function tests^{2,4}	x					x	x	x	x	
PSA²	x	x				x	x	x	x	
Testosterone	x									
⁶⁸Ga-PSMA-11 PET/CT or PET/MR	x ⁵						x			
Disease assessment	x					x	x			

¹ Chemistry panel to include: sodium, potassium, chloride, bicarbonate, BUN/creatinine, glucose, calcium, total bilirubin, AST, ALT, alkaline phosphatase

² Labs may be collected within a window of up to 3 days prior to each dose of pembrolizumab.

³ CBC + differential will be measured on C1D1, C1D8, C1D15, C2D1, C2D8, C2D15, Day 1 of C3+, and additionally as clinically indicated.

⁴ TSH (with reflex free T3/T4) testing to be performed during Screening, Cycle 2 Day 1, and Day 1 of every other cycle thereafter.

⁵ Allow for a 12-week window for the screening PSMA PET scan. PSMA PET at End of Treatment is optional.

	Screening (Day -28 to -1 unless otherwise noted)	Treatment				End of Treatment	Safety Follow up		
		Cycle 1			Cycle 2+ (+/- 3 days unless otherwise noted)		30 Days (+/- 7 days) post-last dose	90 Days (+/- 14 days) post last dose	
		D1 (-3 days)	D2	D8 (+/- 1 day)	D15 (+/- 1 day)	D1 (+/- 3 days)	+ 21 days		
(CT/MR, BS) ⁶									
Tumor Biopsy ⁷	x				x				
Whole blood for immune correlatives ⁸		x			x	x			
¹⁷⁷ Lu-PSMA-617 infusion		x							
SPECT/CT Dosimetry ⁹			x						
Normal Saline		x							
Anti-emetic pre-medication		x							
Pembrolizumab infusion					x				
AE assessment		x	x	x	x	x	x	x	x

⁶ Tumor assessment will be performed with CT chest/and/pelvis + whole body bone scan during Screening, C4D1 (-14d), C7D1 (-14d), and Day 1 (-14d) of every 4 cycles thereafter. If disease progression by RECIST 1.1/PCWG3, confirmatory scans are required \geq 4 weeks following first scan showing progression.

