5.4 Study Calendar – Schedule 3 (¹⁷⁷Lu-PSMA-617 following Pembrolizumab)

	Screening (Day -49 to -21 unless otherwise noted)	Treatment						End of Treatment	Safety Follow up	
		Cycle 1					Cycle 2+ (+/- 3 days unless otherwise noted)	D1 (+/- 3 days)	+ 21 days	30 Days (+/- 7 days) post-last dose
		D-21 (-3 days)	D1 (- 3 days)	D2	D8 (+/- 1 day)	D15 (+/- 1 day)				
Informed consent	x									
Medical history	x									
Baseline conditions	x									
Concurrent medications	x	x	x		x	x	x		x	x
Height	x									
Weight	x	x	x		x	x	x	x	x	x
ECOG Performance status	x	x	x		x	x	x	x	x	x
Physical exam and vital signs	x	x	x		x	x	x	x	x	x
CBC and Serum Chemistry Panel^{1,2}	x	x	x		x	x	x ³	x	x	x
Thyroid function tests^{2,4}	x	x					x	x	x	x
PSA²	x	x	x				x	x	x	x
Testosterone	x									
⁶⁸Ga-PSMA-11 PET/CT or PET/MR⁵	x ⁵							x		

¹ Chemistry panel to include: sodium, potassium, chloride, bicarbonate, BUN/creatinine, glucose, calcium, total bilirubin, AST, ALT, alkaline phosphatase

² Labs may be collected within a window of up to 3 days prior to each dosing of pembrolizumab.

³ CBC + differential will be measured on C1D1, C1D8, C1D15, C2D1, C2D8, C2D15, Day 1 of C3+, and additionally as clinically indicated.

⁴ TSH (with reflex free T3/T4) testing to be performed during Screening, Cycle 1 Day 1, Cycle 2 Day 1, and Day 1 of every other cycle thereafter.

⁵ Allow for a 12-week window for the screening PSMA PET scan. PSMA PET scan at End of Treatment is optional.

Disease assessment (CT/MR, BS) ⁶	x						x	x			
Tumor Biopsy ⁷	x						x				
Whole blood for immune correlates ⁸		x	x				x	x			
¹⁷⁷ Lu-PSMA-617 infusion			x								
SPECT/CT Dosimetry ⁹				x							
Normal Saline			x								
Anti-emetic pre-medication			x								
Pembrolizumab infusion		x	x				x				
AE assessment		x	x		x	x	x	x	x	x	x

⁶ Tumor assessment will be performed with CT chest/and/pelvis + whole body bone scan during Screening, C4D1 (-14d), C7D1 (-14d), and Day 1 (-14d) of every 4 cycles thereafter. If disease progression by RECIST 1.1/PCWG3, confirmatory scans are required \geq 4 weeks following first scan showing progression.

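### Exclusion 1 counts the 28 days after brain-metastasis treatment to C1D1, so in Schedule 3 brain radiotherapy can fall as little as 15 days before the first study drug, against 29 days in Schedules 1 and 2

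*Combined protocol and SAP*

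**What the plan says.** Exclusion 1 in Section 3.3 bars untreated brain metastases and admits treated ones on three conditions:

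- Time since treatment: "Last treatment was > 28 days prior to C1D1".
- Imaging: "No evidence of new/progressive brain metastases is observed on MRI obtained during Screening window".
- Steroids: "Patient is clinically stable without requirement of steroid treatment for at least 14 days prior to first dose of study treatment".

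The opening of Section 3.3 applies the criteria to all patients unless stated otherwise, and nothing is stated otherwise for Schedule 3.

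Section 3.1 puts the first study drug on C1D1 in Schedule 1 (radioligand) and Schedule 2 (radioligand and pembrolizumab together). In Schedule 3 the radioligand is given on C1D1 "following initiation of pembrolizumab on Cycle 1 Day -21".

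Section 5 (Study Procedures) ties screening to the first drug: "Screening assessments must be performed within 28 days prior to the initiation of protocol therapy". The calendars follow this. Section 5.2 has "Screening (Day -28 to -1 unless otherwise noted", and Section 5.4, for Schedule 3, has "Screening (Day -49 to -21 unless otherwise noted".

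Three other exclusions matter here. Exclusion 5 begins "Has received prior radiotherapy within 2 weeks of start of study treatment" and allows a shorter one-week washout only for palliative treatment of non-CNS disease. Exclusion 17 bars external beam radiation in the 14 days before protocol therapy starts. Exclusion 18 bars major surgery in the 28 days before study treatment.

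**The concern.** One exclusion uses two reference days. Its steroid condition runs to the first dose of study treatment, while its time-since-treatment condition runs to C1D1. The two days coincide in Schedules 1 and 2 but are three weeks apart in Schedule 3.

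The other timed washouts in Section 3.3 (inclusion 9; exclusions 5, 7, 12, 14, 17 and 18) all run to study treatment, study drug or protocol therapy. The screening window was moved for Schedule 3, but this 28-day rule was not. No text gives a reason, so it reads as an oversight.

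At stake is even application of a safety criterion across the three schedules. A patient irradiated for brain metastases 15 to 28 days before first study drug is ineligible in Schedules 1 and 2 and eligible, on this criterion, in Schedule 3. The documents give no evidence that this adds risk.

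**Working it through.** The plan states no figure to reproduce; the check is date arithmetic. Day -k is k days before C1D1, with no Day 0, as the calendars imply.

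**Inputs**

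- Exclusion 1: more than 28 days before C1D1, so at least 29 whole days.
- Exclusions 5 and 17: more than 14 days before the start of treatment, so at least 15 whole days. The one-week exception does not apply to CNS disease.
- Lead of the first study drug over C1D1 (Section 3.1): 0 days in Schedules 1 and 2, 21 days in Schedule 3.

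**Minimum interval, brain radiotherapy to first study drug** = max(29 − lead, 15)

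| Schedule | Exclusion 1 alone | Exclusions 5 and 17 | Minimum (whole days) |
|---|---|---|---|
| 1 and 2 | 29 − 0 = 29 | 15 | 29 (more than 28) |
| 3 | 29 − 21 = 8 | 15 | 15 (more than 14) |

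In Schedule 3 the brain-specific rule therefore adds nothing before the first drug for radiotherapy; the general washout sets the limit.

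**Affected dates.** In Schedule 3 the latest permitted date is now Day -(21 + 15) = Day -36. The Schedules 1 and 2 standard would make it Day -(21 + 29) = Day -50. The band is Day -49 to Day -36, which is 49 − 36 + 1 = 14 dates, or 28 to 15 days before first drug.

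**Visit windows.** Section 5.4 lets Day -21 and Day 1 each be up to 3 days early, so the lead can be 18 to 24 days. Exclusion 1 alone then gives 29 − 24 = 5 to 29 − 18 = 11 days. Counting a Day 0 as well (lead up to 25) gives 4. All are below 15, so exclusions 5 and 17 always set the limit and the 14-day band is unchanged.

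**Interval to the radioligand (nominal days).** More than 28 days in Schedules 1 and 2; more than 14 + 21 = 35 days in Schedule 3.

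**Expected number of patients.** Section 1.7.1 reports 14 enrolled in Part A at June 1, 2020, so 18 − 14 = 4 Part A places remained. If Schedule 3 is chosen for Part B, 4 + 25 = 29 places are exposed. The documents do not say how many patients have treated brain metastases or when they were treated. I assume 1% to 5%, with treatment dates spread evenly over the previous 6 to 12 months. The share falling in the band is 14/365 = 0.038 to 14/182.5 = 0.077.

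| Places | Low | High |
|---|---|---|
| 29 (Schedule 3 chosen) | 29 × 0.01 × 0.038 = 0.011 | 29 × 0.05 × 0.077 = 0.11 |
| 4 (not chosen) | 4 × 0.01 × 0.038 = 0.0015 | 4 × 0.05 × 0.077 = 0.015 |

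**The screening MRI.** Day -49 to Day -36 lies inside the Schedule 3 screening window, so the date rules alone no longer guarantee that the MRI follows treatment. This is a minor point: a scan taken before treatment would usually show the lesions that prompted it and fail the imaging condition.

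**The case against.** The best defence is that C1D1 was chosen because it is the radioligand day in all three schedules. Counting brain treatment, usually radiotherapy, to the radiation-bearing drug is coherent, and on that measure Schedule 3 is the stricter one (more than 35 days against more than 28). The protocol also uses C1D1 as a common reference elsewhere: baseline evaluations in Section 3.3, the start of the DLT window, and the rule on focal radiation in Section 4.8. Not every eligibility look-back runs to first dose either; exclusions 13 and 16 use other reference points.

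Further, much protection remains before the first drug in Schedule 3: two weeks since CNS radiotherapy, recovery from radiation toxicity, 14 stable days without steroids, an MRI without new or progressive lesions, and 28 days after major surgery. The expected count rests on outside assumptions. It also ignores these other conditions, so it overstates the number who would actually enter.

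Most of this stands as a limit on importance. It does not remove the point. Nothing in the text ties the 28 days to the radioligand, and the steroid condition beside it protects the first dose of any study treatment, which includes pembrolizumab. Exclusions 13 and 16 are history look-backs, not treatment washouts. The remaining safeguards narrow the difference between schedules but leave it in place.

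**Conclusion.** The point holds, as a minor wording correction. The minimum interval from brain radiotherapy to first study drug is more than 28 days in Schedules 1 and 2 and more than 14 days in Schedule 3, including Part B if that schedule is selected. This reads the start of study treatment in exclusion 5, and of protocol therapy in exclusion 17, as Day -21 in Schedule 3, which is the natural reading. If they were read as C1D1, the Schedule 3 minimum would fall to more than 7 days.

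Under the stated prevalence and timing assumptions the expected number in the affected band is about 0.002 to 0.11, well under one patient in every case. The interval to the radioligand is never below 28 days. No endpoint, DLT rule or analysis changes, and the documents show no added risk.

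**What to change.** In the first condition of exclusion 1, replace *C1D1* with *first dose of study treatment*, the reference day its steroid condition already uses. The minimum then exceeds 28 days to first drug in all three schedules. In Schedule 3 brain treatment must end by Day -50 (more than 28 + 21 = 49 days before C1D1), before screening opens on Day -49, so the screening MRI necessarily follows it. Schedules 1 and 2 are unchanged.

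The cost is a few words in the next amendment and, for a rare Schedule 3 candidate with recent brain radiotherapy, a wait of up to about 14 days.

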3.3 Eligibility Criteria

Patients must have baseline evaluations performed prior to Cycle 1 Day 1 of treatment and must meet all inclusion and none of the exclusion criteria. In addition, the patient must be thoroughly informed about all aspects of the study, including the study visit schedule and required evaluations and all regulatory requirements for informed consent. The written informed consent must be obtained from the patient prior to enrollment. The following criteria apply to all patients enrolled onto the study unless otherwise specified.

Inclusion Criteria

Part A:

- (1) The subject is able and willing to comply with study procedures and provide signed and dated informed consent.
- (2) Male participants who are at least 18 years of age on the day of signing informed consent.

(3) Histologically confirmed prostate adenocarcinoma. *De novo* small cell neuroendocrine prostate cancer will not be allowed due to putative lower PSMA expression in this tumor subtype. Treatment-emergent small cell neuroendocrine prostate cancer detected in metastatic tumor biopsy is not an exclusion.

(4) A minimum of three PSMA-avid lesions on baseline ^{68}Ga -PSMA-11 PET, with positive lesions defined as those with SUV_{max} values greater than liver.

(5) Progressive metastatic castration-resistant prostate cancer by PCWG3 criteria at the time of study entry.

(6) Castrate level of serum testosterone at study entry (< 50 ng/dL). Patients without prior bilateral orchiectomy are required to remain on LHRH analogue treatment for duration of study

(7) Prior progression on at least one second generation androgen signaling inhibitor including abiraterone, apalutamide, darolutamide, and/or enzalutamide.

(8) Adequate hematologic, renal, and liver function, defined as:

- Absolute neutrophil count $> 1.5 \times 10^9/\text{L}$
- Hemoglobin $> 9.0 \text{ g/dL}$
- Platelet count $> 100,000/\text{microliter}$
- Serum creatinine $\leq 1.5 \times \text{ULN}$ or estimated GFR $> 50 \text{ ml/min}$ by Cockcroft-Gault or 24 hour urine collection.
- Total bilirubin $\leq 1.5 \times \text{ULN}$. In patients with known or suspected Gilbert's disease, direct bilirubin $\leq \text{ULN}$.
- Aspartate aminotransferase and alanine aminotransferase $\leq 2.5 \times \text{ULN}$ ($\leq 5 \times \text{ULN}$ in patients with liver metastases).

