(16) Has clinically significant cardiovascular disease including, but not limited to:

- Uncontrolled or any New York Heart Association Class 3 or 4 congestive heart failure.
- Uncontrolled angina, history of myocardial infarction, unstable angina or stroke within 6 months before study entry.
- Clinically significant arrhythmias not controlled by medication. Chronic rate controlled or paroxysmal atrial fibrillation/flutter is not an exclusion to study participation.

- (17) Prior external beam radiation involving $\geq 25\%$ of bone marrow or within 14 days of start of protocol therapy.
- (18) Major surgery within 28 days of study treatment. Note: If participant received major surgery, they must have recovered adequately from the toxicity and/or complications from the intervention prior to starting study treatment.
- (19) Has an active infection requiring systemic therapy
- (20) Has a known history of HIV (screening not required).
- (21) Has a known history of Hepatitis B (defined as Hepatitis B surface antigen [HBsAg] reactive) or known active Hepatitis C virus (defined as HCV RNA [qualitative] is detected) infection (screening not required)
- (22) Has a known history of active TB (Bacillus Tuberculosis).
- (23) Has known psychiatric or substance abuse disorders that would interfere with cooperation with the requirements of the trial.
- (24) Any condition that, in the opinion of the Principal Investigator, would impair the patient's ability to comply with study procedures
- (25) History of bleeding diathesis and not currently on anti-coagulation therapy that cannot be safely discontinued for the tumor biopsy procedure.

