⁷ Tumor biopsy will be performed during Screening and within 7 days preceding C2D1 visit. Screening biopsy must be performed prior to initiation of study treatment but is not subject to 28-day screening window. Bone biopsies are acceptable if no soft tissue lesion is amenable for biopsy. The same lesion should be selected for the follow up biopsy whenever feasible.

⁸ Whole blood (40 mL in Na-Heparin green top tube) will be collected on C1D1 (pre-dose), C2D1 (pre-dose), C3D1 (pre-dose), on Day 1 of every 3 cycles thereafter (e.g. C6D1, C9D1, etc), and at the time of disease progression

⁹ SPECT/CT dosimetry scan is optional.

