⁷ Tumor biopsy will be performed during Screening and within 14 days preceding C3D1 visit. Screening biopsy must be performed prior to initiation of study treatment but is not subject to 28-day screening window. Bone biopsies are acceptable if no soft tissue lesion is amenable for biopsy. The same lesion should be selected for the follow up biopsy whenever feasible. PSMA-avid lesion should be prioritized for biopsy; non-PSMA avid lesion may be used if no PSMA-avid lesion is accessible.

⁸ Whole blood (40 mL in Na-Heparin green top tube) will be collected on C1D-21 (pre-dose), C1D1 (pre-dose), C2D1 (pre-dose), C3D1 (pre-dose), on Day 1 of every 3 cycles thereafter (e.g. C6D1, C9D1, etc), and at the time of disease progression.

⁹ SPECT/CT dosimetry scan is optional.

6 Reporting and Documentation of Results

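### Exclusion 25 is inverted in its anticoagulation half: it does not exclude a patient whose anticoagulation cannot be stopped for biopsy

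*Combined protocol and SAP*

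**What the plan says.** The lead-in to Section 3.3 (Eligibility Criteria) states that patients "must meet all inclusion and none of the exclusion criteria", and that the criteria apply to everyone enrolled unless otherwise specified. Exclusion 25 reads: "History of bleeding diathesis and not currently on anti-coagulation therapy that cannot be safely discontinued for the tumor biopsy procedure".

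Two other criteria bear on biopsy without naming bleeding risk:

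- Inclusion 13: "Patients willing to undergo tumor biopsy and have at least one lesion safely accessible to tumor biopsy".
- Exclusion 24: "Any condition that, in the opinion of the Principal Investigator, would impair" the patient's ability to comply with study procedures.

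Biopsies are scheduled in all three calendars. Footnote 7 of Section 5.2 (Schedule 1) says: "Tumor biopsy will be performed during Screening and within 7 days preceding C2D1 visit". Footnote 7 of Section 5.3 (Schedule 2) has the same sentence. For Schedule 3, footnote 7 of Section 5.4 says: "Tumor biopsy will be performed during Screening and within 14 days preceding C3D1 visit". None of these footnotes marks the biopsy as optional, whereas footnote 9 in each calendar does so for the SPECT/CT dosimetry scan.

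**The concern.** The phrase about not being on anticoagulation reads like an entry condition, but it sits in a list of conditions that bar entry. Joined by *and* to the diathesis clause, it narrows the exclusion when it should widen it. The result is a perverse ordering: a man with a diathesis alone is excluded, while a man with a diathesis and anticoagulation that cannot be stopped is not.

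What is at stake is biopsy safety. Each patient is scheduled for one biopsy at screening and one on treatment. The second follows ¹⁷⁷Lu-PSMA-617, for which Section 4.1.8 lists thrombocytopenia as an adverse reaction. Anticoagulated candidates are plausible, since exclusion 16 states: "Chronic rate controlled or paroxysmal atrial fibrillation/flutter is not an exclusion to study participation". An eligibility checklist that copies exclusion 25 literally would clear the patients it should stop.

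**Working it through.** No calculated figure is involved, so the check is one of logic.

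**Inputs**

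- D: the patient has a history of bleeding diathesis (exclusion 25, first clause).
- A: the patient is on anticoagulation that cannot be safely stopped for biopsy (exclusion 25, second clause, without the negation).
- Operating rule: an exclusion bars a patient only when it is true of him (lead-in to Section 3.3).

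**Candidate rules**

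- As written: excluded if D and not A.
- Evident intent: excluded if D or A.
- List reading, with *and* taken as joining two separate exclusions: excluded if D or not A.
- Partial repair, with only *not* deleted: excluded if D and A.

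| D | A | As written | Evident intent | List reading | Only *not* deleted |
|---|---|---|---|---|---|
| no | no | not excluded | not excluded | excluded | not excluded |
| no | yes | not excluded | excluded | not excluded | not excluded |
| yes | no | excluded | excluded | excluded | not excluded |
| yes | yes | not excluded | excluded | excluded | excluded |

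**Results**

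1. As written, 1 of 4 combinations is excluded; under the evident intent, 3 of 4. They differ in 3 − 1 = 2 rows, exactly the two with A = yes. The diathesis-only row is handled correctly.
2. The list reading does not rescue the text. It would exclude every patient with neither risk, which cannot be meant, and it would still admit an anticoagulated patient without a diathesis. All it changes for anticoagulated patients is the row with both risks.
3. Deleting only *not* also excludes 1 of 4, and it misses both single-risk rows.

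**Is the safeguard stated elsewhere?** No other item in Section 3.3 mentions anticoagulation or bleeding diathesis. The supportive-care and concomitant-medication text in Section 4.8 does not mention anticoagulants. Inclusion 13 turns on whether a lesion can be reached safely, and exclusion 24 on the investigator's opinion about compliance.

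**The case against.** The strongest reply is that little is likely to go wrong in practice. Inclusion 13 is mandatory, and an investigator could fairly judge that a man whose anticoagulation cannot be stopped has no lesion that is safe to biopsy. Exclusion 24 offers a second route. The closing words of exclusion 25 also make its purpose obvious, and a clinician is unlikely to admit a man with a diathesis because he is also irreversibly anticoagulated. The count of 1 against 3 weighs logical combinations equally and says nothing about how often each occurs. Allowing atrial fibrillation makes anticoagulated patients plausible, but does not show that any has therapy that cannot be interrupted. Finally, the intended rule is inferred; the protocol nowhere states it.

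All of this stands as a limit on consequence. It does not make the sentence correct. The two backstops are discretionary and neither names the risk, so the explicit safeguard is missing even if protection is not wholly lost. That a reader must override the literal text to reach the purpose is the reason to correct it.

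**Conclusion.** The concern holds. Exclusion 25 is wrong as written: its anticoagulation half works in reverse. The error is minor. The number of patients affected is not given and could be zero, and the trial's statistical results do not depend on it.

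That the literal text fails to exclude the anticoagulated patient follows from the wording alone and is held with high confidence. The comparison with three excluded combinations rests on one assumption, that either risk by itself was meant to exclude. This is the most plausible reading, but the clinical team has to confirm it.

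**What to change.** In exclusion 25, replace the words *and not* with a comma and *or*, leaving the rest of the sentence unchanged. A history of bleeding diathesis, or current anticoagulation that cannot be safely stopped for biopsy, would then each exclude on its own. Any eligibility checklist derived from the criterion should be changed to match.

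The cost is one line in the next amendment, applied to future enrolments. Sample size, schedules and analysis need no change.
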